6.4. EMBEDDED QUALITATIVE STUDY

Participants will be invited by the research team to receive further information about the qualitative sub-study at the time of consent to the main trial. Those who have agreed to be receive more information will then be contacted by a member of the qualitative research team within 2 weeks to ask if they would like to participate in the sub study. The aims of the qualitative study are to explore the patients' experiences of being recruited to a randomised trial of anti-TNF injection for frozen shoulder, of the treatment received and follow-up schedule, and to understand what helps participant recruitment to the trial intervention.

After obtaining signed consent individual telephone interviews will be conducted within 4 weeks of either intervention delivery by a qualitative researcher using a semi-structured interview guide with open-ended questions. All participants will be asked to reaffirm their consent before the start of the interview. We aim to interview a purposive sample of up to 15 participants (or until we reach data saturation, the qualitative researcher will also be blinded) to provide variability for age, gender, ethnicity and geographical representation. Interviews will be audio recorded using a password protected digital recorder and field notes will be taken). Immediately after each interview, the audio files will be saved under unique non-identifiable study IDs on the Anti-Freaze F secure eTMF. The audio files will be transcribed verbatim by an external transcription service approved by the University of Oxford. The audio files and transcripts will be sent and returned using a password protected folder via a suitably secure method. Once returned the transcribing company will not retain any files. The transcripts will be checked against the audio-files and all identifiable information such as names of people or places will be removed. The de-identified transcripts will be stored using the study IDs. The transcripts will be uploaded into QSR NVivo analysis software version 12. As these are considered source data copies of the anonymised typed transcripts and original audio recordings will be kept in a secure place within the University of Oxford for a maximum of 5 years and then destroyed. An inductive thematic analysis will be undertaken to develop categories and themes (51). The study findings will be reported following the Standards for Reporting Qualitative Research (SRQR) guidelines (52).

6.5. PROGRESSION CRITERIA

Progression criteria for the future definitive trial will be judged using a traffic light system whereby 'Green' indicates it is feasible to proceed to a definitive trial with the current procedures, 'Amber' indicates modification to one or more aspect of the study is required before proceeding to the future definitive trial, and 'Red' indicates it is not feasible (53). The decision to progress to a future definitive trial will be made by the Trial Management Group in conjunction with the Trial Steering Committee, based on the criteria in Table 4. It will also be informed by findings from the embedded qualitative study and any potential signal of efficacy due to improvement in range of shoulder motion as a result of anti-TNF injection.

Table 4: Progression criteria

	Green	Amber	Red
Feasibility to recruit: % of potentially eligible patients with frozen shoulder screened across 5	≥33%	≥20% to 32%	<20%

sites in 12 months eligible for recruitment			
Success of consent process: % of eligible participants consented	≥33%	≥20% to 32%	<20%
Intervention delivery: % of participants receive 1 st injection as randomised within specified timeframe	≥75%	≥50% to 74%	<50%

7. MONITORING METHODS

7.1. DATA MONITORING

7.1.1. Data Monitoring

A monitoring plan, including risk assessment, will be developed according to OCTRU SOPs. The monitoring activities will be based on the outcome of the risk assessment and may involve central monitoring or site monitoring visits.

7.2. SAFETY REPORTING

7.2.1. Definitions

Adverse Event (AE)	Any untoward medical occurrence in a clinical trial participant administered a medicinal product and which does not necessarily have a causal relationship with this treatment.
Adverse Reaction (AR)	An untoward and unintended response in a participant to an investigational medicinal product that is related to any dose administered to that participant. The phrase “response to an investigational medicinal product” means that a causal relationship between a trial medication and an adverse event is at least a reasonable possibility, i.e., the relationship cannot be ruled out. All cases judged by either the reporting medically qualified professional or the sponsor as having a reasonable suspected causal relationship to the trial medication qualify as adverse reactions.
Serious Adverse Event (SAE)	An SAE is any untoward medical occurrence that: 1. results in death, 2. is life-threatening,

	
3. requires inpatient hospitalisation or prolongation of existing hospitalisation,
 
4. results in persistent or significant disability/incapacity, or
 
5. consists of a congenital anomaly or birth defect.
 
Other “important medical events” may also be considered serious if they jeopardise the participant or require an intervention to prevent one of the above consequences.
 
The term “life-threatening” in the definition of “serious” refers to an event in which the participant was at risk of death at the time of the event; it does not refer to an event which hypothetically might have caused death if it were more severe.

Serious Adverse Reaction (SAR)	An adverse event that is both serious and, in the opinion of the reporting investigator, is believed with reasonable probability to be due to one of the trial treatments, based on the information provided.
Suspected Unexpected Serious Adverse Reaction (SUSAR)	A serious adverse reaction, the nature and severity of which is not consistent with the information about the medicinal product in question set out in the summary of product characteristics (SmPC) for that product.

7.2.2. Causality

The relationship of each adverse event to the trial medication must be determined by a medically qualified individual according to the following definitions:

Relationship to intervention	Attribution (causality)	Description
Unrelated	Unrelated	The AE is clearly NOT related to the intervention
	Unlikely	The AE is doubtfully related to the intervention
Related	Possible	The AE may be related to the intervention
	Probable	The AE is likely related to the intervention
	Definite	The AE is clearly related to the intervention

7.2.3 Procedures for recording adverse events

The safety profile of adalimumab is well known, with the most common adverse reactions being mild injection site reactions. The Common Terminology Criteria for Adverse Events (CTCAE) v5.0 (will be used to guide recording Adverse Events including grading of the event. Only clinician assessed AEs, graded 3 and above, occurring during the trial for each participant, from their consent until the 3

month follow up and that are considered related to the IMP will be recorded on the CRF. Participants will be asked by the treating clinician at their 2nd injection visit if they have experienced any AEs as a result of their 1st injection. Similarly, participants will be asked if they have experienced any AEs as a result of their 2nd injection at the 3 month follow up appointment. Based on the information provided by the participant the treating clinician will then make an assessment as to whether it should be recorded as an AE grade 3 or above. The capture of all AEs in the trial CRFs is not deemed necessary due to the period of time for which the IMP has had a marketing authorisation and it's well established safety profile.

The following information will be recorded: adverse event term and grade, date of onset and end date, severity, assessment of relatedness to IMP/injection procedure, other suspect drug or device, action taken and outcome. Follow-up information should be provided as necessary. AEs considered related to the trial medication injection as judged by a medically qualified investigator will be followed either until resolution, or the event is considered stable. It will be left to the Investigator's clinical judgment to decide whether or not an AE is of sufficient severity to require the participant's removal from treatment. A participant may also voluntarily withdraw from treatment due to what he or she perceives as an intolerable AE. If either of these occurs, the participant must be given appropriate care under medical supervision until symptoms cease, or the condition becomes stable. Adverse events occurring as a result of the physiotherapy leaflet issued in the trial will not be recorded as part of the trial. The trial risk assessment identified no safety concerns, as advice and exercises given will be routine exercises that are used in standard care for this population. (16).

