Secondary objectives	
To assess the follow up rates and viability of patient reported outcome measures and range of shoulder motion at 3 months follow up for a definitive trial:
 
Patient reported:
 
 • Pain and function (Shoulder Pain And Disability Index) • Pain (Shoulder Pain And Disability Index, 5-item subscale) • Function (Shoulder Pain And Disability Index, 8-item subscale) • Psychological factors (Fear Avoidance Belief Questionnaire) • Pain Self Efficacy Questionnaire • Sleep disturbance (Insomnia Severity Index) • Return to desired activities (Patient-reported) • Global impression of change (Likert scale) • Participant Range of Movement Questionnaire • Healthcare resource use • Adverse events graded 3 or above (clinician assessed) related to intra-articular injection of adalimumab in the shoulder 
Clinician assessed:
 
 • Shoulder range of movement 
Embedded qualitative sub-study (optional participation):
 
 • To explore the patients' experiences of being recruited to a randomised trial of anti-TNF injection for frozen shoulder. • To understand what helps or hinders participant recruitment to the trial intervention.
Data Sharing statement	
Summary results data will be available on the trial registration database within 12 months of the end of the trial. Requests for data (anonymised trial participant level data) will only be provided at the end of the trial to external researchers who provide a methodologically sound proposal to the trial team (and who will be required to sign a data sharing access agreement with the Sponsor) and in accordance with the NIHR guidance. After the end of the study a anonymised study dataset will be created and stored for as long as it is useful, and may be shared with other researcher upon request (as defined above). Participant consent for this is included in the informed consent form for the study.

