The palmar nodules in patients with Dupuytren's disease are readily identifiable clinically. However, the only means of accurately delivering adalimumab to the involved areas in patients with frozen shoulder is by ultrasound guidance. Furthermore, due to the larger area involved, we will use 160mg of adalimumab in 3.2ml. It is possible that some patients may fail to gain significant improvement in symptoms following administration of 160mg of adalimumab. The half-life of adalimumab is 2 weeks and up to 160mg can be administered as a loading dose in patients with inflammatory disorders such as Crohn's disease (<https://bnf.nice.org.uk/drug/adalimumab.html#indicationsAndDoses>). Patients will receive a second injection of adalimumab (80mg in 1.6ml) at 2-3 weeks after the initial injection.

We are not aware of any other trials for frozen shoulder investigating the efficacy of using a drug targeting a defined inflammatory cytokine. The anti-TNF drugs have a very strong safety profile, having been used in over 10 million people, adalimumab in over 5 million, and more than 25,000 patients have been recruited to trials of adalimumab, which is approved for 9 different disorders. In these, only 0.2% of patients with chronic inflammatory disorders discontinued long-term use of the drug, which is administered every 2 weeks, due to adverse effects. Anti-TNF drugs not routinely administered as an intra-articular injection, although there are a few reports of outcomes in patients with inflammatory or osteoarthritis (28-31). We are not aware of any trials where intra-articular injection of adalimumab has been used in people with frozen shoulder. Adalimumab is not currently licenced for use as an intra-articular injection for pain-predominant early-stage frozen shoulder and therefore will be used off license for the purposes of this trial. Therefore, as part of this feasibility trial we will also assess the safety of anti-TNF injection when given as an intra-articular injection, by recording any clinician reported grade 3 or above adverse events.

Administration of adalimumab should not pose any risks in relation to COVID-19 vaccinations or to patients who may have contracted COVID-19. None of the approved vaccines involve live viruses. Adalimumab was being trialled in UK care home residents for the treatment of COVID-19, although this trial has been closed because of the lack of eligible participants due to the success of the

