Adalimumab is not currently licenced for use as an intra-articular injection for people with pain-predominant early-stage frozen shoulder and will be used off license for the purposes of this trial. Therefore, as part of this feasibility trial we will also assess the safety of anti-TNF injection and record Adverse Events assessed by a clinician to be grade 3 or above as a result of the IMP injection.

Clinician assessed outcome:

- Shoulder range of movement.

[figure not shown]
Embedded qualitative sub-study (optional participation):

- To explore the patients' experiences of being recruited to a randomised trial of anti-TNF injection for frozen shoulder.
- To understand what helps or hinders participant recruitment to the trial intervention.

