4.4.2. Outcomes

Outcomes (Table 2) will be collected at baseline and at 3-months to assess the feasibility of collecting these in a future definitive trial and to obtain the variability estimates required for estimation of the sample size of the definitive trial. Patient reported outcomes will include shoulder pain and function measured using the SPADI scale (primary outcome for definitive trial) (38, 39); sub-domains of pain (SPADI 5-item pain subscale), function (SPADI 8-item disability subscale) (38, 39); shoulder range of motion (Participant Shoulder Movement Questionnaire); psychological factors (Fear Avoidance Belief Questionnaire) (40); pain self-efficacy questionnaire (41); sleep disturbance (Insomnia Severity Index) (42); patient global impression of change (43); return to desired activities; additional health resource use for index shoulder (e.g. consultation with primary and secondary care, additional physiotherapy, injection use, or alternative therapies).

The choice of outcome measures is based on OMERACT 2016 core outcome set for shoulder disorders (44) and a systematic review of core outcomes used in studies of frozen shoulder (45).

At the 3-month follow up, a blinded outcome assessor will collect an objective measure of shoulder function and performance:

- Participants will undergo measurement of range of motion of the shoulder, including active flexion, extension, abduction internal and external rotation, limitation of which has been shown to be pathognomonic of frozen shoulder in the absence of glenohumeral arthritis (46).

Table 2: Summary of patient outcomes assessed

Outcome	Measurement
Pain and function	Shoulder Pain and Disability Index (SPADI) (38, 39) 13-item total scale
Pain	Shoulder Pain and Disability Index (SPADI) (38, 39) 5-item subscale
Function	Shoulder Pain and Disability Index (SPADI) (38, 39) 8-item subscale
Shoulder range of motion	Participant Shoulder Movement Questionnaire
Psychological factors	Fear Avoidance Belief Questionnaire – physical activity 5-item subscale (40) Pain Self-efficacy questionnaire (short form) (41)
Sleep disturbance	Insomnia Severity Index (42)
Global impression of treatment	Patient-rated Likert scale (43)
Return to desired activities	Patient-reported return to desired activities, including work, social life and sport activities
Health resource use	Patient-reported

Adverse Events	Any Grade 3 or above AEs that have occurred from Consent up until the 3 month Follow up.
----------------	--

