See section 7.2. SAFETY REPORTING for safety data collection

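### The adverse-event outcome is stated two ways (any grade 3+ event, or only related ones), and the questions in Section 7.2.3 do not match the 3-month assessment scheduled for everyone

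*Combined protocol and SAP*

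**What the plan says.** Two definitions of the outcome are in the current text.

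- **Any event.** Table 2 (Section 4.4.2) and Table 3 (Section 6.1.1) list "Any Grade 3 or above AEs that have occurred from Consent up until the 3 month Follow up". Section 3.1.3 (Choice of comparators) says safety will be assessed "by recording any clinician reported grade 3 or above adverse events".
- **Related events only.** Section 7.2.3 limits the CRF to grade 3+ events "that are considered related to the IMP will be recorded on the CRF". The Trial Summary has "Adverse events graded 3 or above (clinician assessed) related to intra-articular injection of adalimumab in the shoulder", and Section 3.2 undertakes to "record Adverse Events assessed by a clinician to be grade 3 or above as a result of the IMP injection".

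Below Table 2 stands the pointer "See section 7.2. SAFETY REPORTING for safety data collection". Section 7.2.1 defines an adverse event as one that "does not necessarily have a causal relationship with this treatment" and calls a related event an adverse reaction. Section 6.3 promises a summary of adverse events and serious adverse events by group and overall, without saying which set.

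On questioning, Section 7.2.3 has participants "asked by the treating clinician at their 2nd injection visit if they have experienced any AEs as a result of their 1st injection", and asked about the second injection at the 3-month appointment. The timeline in Section 4.5 and the schedule in Appendix 2 tick a grade 3+ assessment at 3 months, with no condition on the number of injections.

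On serious events, Section 7.2.4 requires related ones to be reported within 24 hours of site knowledge, from consent to 28 days after the last injection. Section 5.4 plans emergency unblinding for serious reactions up to 3 months after the last injection.

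**The concern.** Section 3.1.3 gives the off-licence intra-articular route as the reason for assessing safety in this trial. The record should therefore match the stated outcome. Under the rule in Section 7.2.3, whether an event enters the comparison between arms depends on a causality judgement, and an event that was never recorded cannot be re-judged. Section 7.2.1 lets either the reporting professional or the sponsor classify an event as a reaction. The sponsor cannot do so for events that the site has screened out.

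The two questions, read literally, pass over part of the randomised population. A difference between the reporting windows also means that a serious related event late in follow-up might reach the Trial Office later than it need. The independent oversight committee (Section 9.2.3) gives its safety advice from the data arising from the trial.

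**Working it through.** The plan gives no figure to reproduce here. The check is a comparison of text plus day counts.

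**1. Can the tabulated outcome be produced?** Tables 2 and 3 need every grade 3+ event. Section 7.2.3 puts on the CRF only the related ones. Unrelated grade 3+ events have no place on the form, so the tabulated outcome cannot be derived. Two details fit related-only recording poorly: collection starts at consent, before any injection, and Section 7.2.2 provides categories for unrelated and unlikely events that the relatedness field in 7.2.3 would never hold.

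**2. Who falls outside the questions in 7.2.3?**

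| Participant | Injection-1 question (second injection visit) | Injection-2 question (3 months) |
|---|---|---|
| Two injections, event before the second visit | covered | covered |
| Two injections, late effect of injection 1 | already asked | asks about injection 2 only |
| One injection (declined; related grade 3+ event; positive TB or hepatitis B test) | no such visit | no second injection |
| Returns the questionnaire only (Section 6.1.2) | covered if the visit was held | method not stated |

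Single-injection participants are still followed to 3 months (Sections 4.3.1, 5.3 and 6.1.3). The documents give no expected rate of missed second injections. If it were 5-20% (an assumption), 84 × 0.05 = 4.2 to 84 × 0.20 = 16.8, or about 4-17 people. They would still be due the scheduled 3-month assessment.

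**3. How far apart are the windows?** Inputs: first injection on day 0-14 after randomisation (Section 4.3.1, as an ideal); second injection 14-21 days later (Section 4.5 footnote); serious-event duty to last injection + 28 days (Section 7.2.4); follow-up 3 months after randomisation (Section 6.1.2), taken as day 91.

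Gap = 91 − (day of last injection + 28).

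| Case | Last injection | Duty ends | Gap |
|---|---|---|---|
| Two injections, text rules | day 14-35 | day 42-63 | 28-49 days (4-7 weeks) |
| Two injections, second at 4-5 weeks (Section 4.5 column) | day 28-35 | day 56-63 | 28-35 days (4-5 weeks) |
| One injection | day 0-14 | day 28-42 | 49-63 days (7-9 weeks) |

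If 3 months means day 84, each gap is 7 days shorter. The gap closes only if the first injection slips to day 91 − 28 − 21 = 42 (3-week spacing) or day 91 − 28 − 14 = 49 (2-week spacing). The unblinding window in Section 5.4 runs to about day 14 + 91 = 105 to day 35 + 91 = 126 with two injections, past both of the others.

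**4. Scale.** With 84/2 = 42 per arm, one event recorded or not moves an arm's rate by 1/42 = 2.4 percentage points. How many events are affected is unknown.

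**The case against.** The strongest reply is that related-only recording is deliberate. Section 7.2.3 gives its reason (a marketed drug with a known safety profile), Section 7.2.4 says unrelated serious events need not be reported, and Table 2 points to Section 7.2. This stands: all-cause recording cannot be demanded as the only remedy. It does not remove the contradiction, because the pointer does not narrow the wording of Tables 2 and 3, and Section 3.1.3 remains unqualified.

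Four stronger readings are tempting, and the documents do not support them.

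- *Single-injection participants get no adverse-event assessment.* Section 4.5 and Appendix 2 schedule one at 3 months for everyone, and Table 3 lists adverse events at that time. The fault is that the wording of 7.2.3 does not deliver that schedule. A participant stopped for a related grade 3+ event has also, by definition, had that event identified.
- *The unblinded injector judges the events.* Section 7.2.3 does not say who the treating clinician is. Section 5.2 bars the injector from further trial-specific assessment and gives clinician-assessed outcomes at 3 months to a blinded team member. There is a conflict only if the injector is meant.
- *The shorter serious-event window is an error, or late serious events are lost.* Differing windows are not wrong in themselves. Related grade 3+ events still reach the CRF up to 3 months, often by direct entry into the database (Section 6.2), and the SUSAR duty in Section 7.2.5 has no end date. What remains is that the fields listed in 7.2.3 include no seriousness item, and that the SUSAR clock starts only once the Trial Office knows of the event.
- *The comparison between arms is biased.* Participants are blinded, and a possible link already counts as related (Section 7.2.2). No direction or size can be inferred.

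**Conclusion.** The contradiction in the outcome definition is established on the text: following Section 7.2.3, the outcome in Tables 2 and 3 cannot be reported, and the Section 6.3 summary would carry the wrong name. The mismatch between the questions in 7.2.3 and the schedules is also established, as is the silence on how events are obtained from those who only return the questionnaire. The difference in windows is a secondary point for explanation: 28-49 days with two injections and 49-63 days with one, assuming follow-up at day 91 and injections on schedule.

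The effect on the results is of unknown size and direction and may be nil. Section 7.2.4 expects events to be rare, and no criterion in Table 4 uses them. The point should still be fixed, because events not recorded cannot be recovered at analysis.

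**What to change.** 1. **One definition throughout.** Either record all grade 3+ events, use the relatedness field already listed in Section 7.2.3, and summarise all-cause and related events by arm; or keep related-only recording, correct Section 3.1.3 and Tables 2 and 3, and label the Section 6.3 summaries of adverse and serious adverse events as related events.
2. **Questions that match the schedules.** Reword Section 7.2.3 so that every participant is asked about any adverse event since the last visit, at the second injection visit if it is held and at 3 months, whatever the number of injections. Put the same question to those who only return the questionnaire.
3. **Seriousness and windows.** Add a serious yes/no item to the adverse-event CRF, and reconcile or explain the windows in Sections 7.2.3, 7.2.4 and 5.4.
4. **Assessor.** State who the treating clinician in Section 7.2.3 is, and record that person's blinding status. Reconcile this with Section 5.2 and with Section 4.3.1, whose rule on the second injection needs grade and relatedness to be known beforehand; a causality review after that injection would come too late for it. No clinical rule is proposed here.

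Cost: protocol and CRF wording, an item for seriousness and one for blinding status, and a question for questionnaire-only participants. If all-cause recording is chosen, there would be a few extra entries, given that events are expected to be rare. No new visits are needed.

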4.3. INTERVENTIONS

4.3.1. Adalimumab/Placebo Injection

Eligible participants will be allocated to receive either an intra-articular injection of adalimumab (160mg in 3.2ml for the first injection, 80mg in 1.6ml for second injection) or placebo (normal saline [0.9% NaCl] 3.2ml for the first injection and 1.6ml for the second injection). The dose of 160mg followed by 80mg two weeks later was selected as this is the approved loading dose in patients with inflammatory bowel disease. The shoulder joint capsule is vascular and we anticipate that absorption into the blood stream will follow similar kinetics as when the adalimumab is administered subcutaneously. The injection will be given into the anterior shoulder joint space in the rotator cuff interval where there is maximal inflammation of the capsule and synovium, under guided ultrasound. The injection treatment is to be given within ideally 2 weeks after randomisation by an appropriately qualified practitioner, with experience of treating frozen shoulder by ultrasound guided injection who is appropriately delegated to do so. The practitioner will be either a GP with a specialist interest in musculoskeletal conditions, rheumatologist, extended scope physiotherapist, orthopaedic surgeon, sonographer or radiologist, dependant on the local service provision at site. The practitioner will need to confirm that the participant is still in the pain predominant phase before administering the first injection. If the practitioner deems that the participant is no longer in the pain predominant phase, the participant will not receive the injection and the reason will be recorded on the trial specific injection treatment log; the participant will still be included in the 3-month follow up assessment.

If a participant has symptoms of COVID-19, tests positive for COVID-19 or is self-isolating due to government guidelines and is unable to attend for either injection, the visit will be delayed until they

receive confirmation of a negative test result or have recovered as long as they remain in the pain predominant stage. If a participant is no longer considered to be in the pain predominant stage and is unable to have the injections this will be recorded on the injection CRF and will be recorded as a withdrawn from treatment but they will continue to be followed up at 3 months.

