5.2. BLINDING

Study participants will be blinded to their treatment allocation. The clinician delivering the treatment injection will not be blinded to the treatment allocation as they will be required to prepare and administer the IMP. They will not be involved with any further trial-specific assessment of the participant. They will be educated on the importance of maintaining the blind of both study participants and the rest of the site staff. All other site staff, except pharmacy staff, will be blinded. The clinician assessed outcomes at the 3 month follow-up clinic visit will be undertaken by a blinded member of the clinical team at site. The trial statistician, Trial Office staff member undertaking checks of dispensed medication, and data entry personnel will not be blinded to the treatment allocation. The remaining members of the trial management team, including the staff conducting the qualitative interviews will be blinded to treatment allocation until after the data analysis is complete.

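### Section 7.2.3 lets the unblinded injector elicit and grade adverse events, which section 5.2 rules out, and nothing requires relatedness to be judged blind

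*Combined protocol and SAP*

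**What the plan says.** Section 5.2 (Blinding) says that the clinician who gives the injection also prepares it and so knows the allocation. It adds: "They will not be involved with any further trial-specific assessment of the participant". All other site staff except pharmacy are to be blinded, and a blinded member of the site team makes the clinician-assessed outcomes at 3 months.

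Section 7.2.3 (Procedures for recording adverse events) says of events after the first injection: "Participants will be asked by the treating clinician at their 2nd injection visit if they have experienced any AEs as a result of their 1st". A parallel question is asked at 3 months about the second injection, without naming who asks it. For both, "the treating clinician will then make an assessment as to whether it should be recorded as an AE grade 3 or above". The same section limits recording to events of grade 3 or above "that are considered related to the IMP will be recorded on the CRF".

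Tables 2 and 3 (sections 4.4.2 and 6.1.1) describe the outcome without that condition: "Any Grade 3 or above AEs that have occurred from Consent up until the 3 month Follow up".

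On causality, section 7.2.2 says: "The relationship of each adverse event to the trial medication must be determined by a medically qualified individual". Section 7.2.3 also speaks of a medically qualified investigator, and section 7.2.4 of a medically qualified doctor for serious events. None of the three mentions blinding.

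Section 4.3.1 lists who may inject: a GP with a musculoskeletal interest, or "rheumatologist, extended scope physiotherapist, orthopaedic surgeon, sonographer or radiologist, dependant on the local service provision at site". It also says that a related event of grade 3 or above after the first injection rules out the second.

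**The concern.** Section 3.3 calls the trial double blind. Section 3.1.3 (Choice of comparators) and section 3.2 make the safety of the unlicensed intra-articular route one of the things to be assessed, and section 6.3 summarises adverse events per group. That summary is a fair comparison only if events are sought, graded and filtered in the same way in both arms. If the person asking knows whether the participant had adalimumab or saline, the probing, the grade and the decision to record can all depend on the arm.

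Under 7.2.3 an event below grade 3, or one not considered related, is not recorded at all, so a misjudgement could not be corrected at analysis. A second consequence follows from section 4.3.1: the same judgement feeds the decision on the second injection. The number receiving that injection belongs to a primary feasibility objective (section 3.2) and is reported per group (section 6.3).

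**Working it through.** The plan gives no figure to reproduce, so the check is a comparison of passages.

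1. **Who is the treating clinician at the second-injection visit?** The protocol does not define the term. Section 4.6.3 uses a similar term, treating practitioner, for the person who makes the clinic diagnosis, so another reading is possible. But Appendix 2 lists only three activities at that visit: local anaesthetic, trial injection and assessment of adverse events. No section places another clinician there. The injector is the natural reading, and 7.2.3 does not exclude it.

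2. **Does this conflict with section 5.2?** On that reading, yes. Asking about events after the first injection and deciding whether they count as grade 3 or above is trial-specific assessment after an injection has been given. Section 5.2 bars the injector from it.

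3. **The 3-month visit.** Section 7.2.3 again gives the recording decision to the treating clinician. Section 5.2 gives clinician-assessed outcomes at that visit to a blinded team member, and the trial summary marks adverse events of grade 3 or above as clinician assessed. The conflict is less sharp here, because 7.2.3 does not say who asks and the injector has no stated task at that visit.

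4. **Who judges relatedness?** Sections 7.2.2, 7.2.3 and 7.2.4 all require medical qualification and none requires blinding. If the injector is a rheumatologist, orthopaedic surgeon or radiologist, that person meets the requirement while knowing the arm. If the injector is an extended-scope physiotherapist or a sonographer, a doctor must judge relatedness, but no hand-over is described. Since a related event bears on the second injection, the judgement is needed before that injection is given, at the visit where the unblinded injector is present.

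5. **What is recorded?** Section 7.2.3 requires both grade 3 or above and relatedness. Tables 2 and 3 require only the grade. How far a relatedness judgement can remove an event from the data depends on which applies.

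6. **Is there a second check?** Section 7.2.4 adds review by a nominated person and the chief investigator, lets either side's finding of related prevail, and presumes relatedness if the site gives no assessment. This covers reported serious events. Serious events that a site considers unrelated need not be reported, and no second causality review is described for non-serious events of grade 3 or above.

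7. **Scale.** The target is 84 randomised 1:1, so 84 / 2 = 42 per arm. One event wrongly included or left out moves an arm's rate by 1 / 42 = 2.4 percentage points. This shows how sensitive the summary is to a single event. It does not estimate bias.

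**The case against.** The strongest reply is that 7.2.3 does not say what a hurried reader might infer. It gives the treating clinician the decision on grade and recording, and does not expressly give that person attribution. Causality belongs to a medically qualified person, who could be the principal investigator or another doctor at the site, and section 5.2 keeps such people blinded. That stands: the documents do not support saying that the protocol has relatedness judged with knowledge of the arm. They show only that it is not prevented.

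A reader might also infer from the list of permitted injectors that someone without a medical qualification could judge relatedness. Sections 7.2.2, 7.2.3 and 7.2.4 exclude that. What remains is the undescribed hand-over.

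The consequences are also limited. Section 6.3 plans a summary of adverse events and no test. Neither adverse events nor second-injection counts appear in the progression criteria of Table 4, where the delivery criterion concerns the first injection. Section 7.2.4 expects events to be rare, and reported serious events receive the further review described above. These points lower the priority of the issue, but they do not resolve the conflict between 5.2 and 7.2.3.

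**Conclusion.** The point holds as an internal contradiction that affects blinding, and it should be fixed. As written, 7.2.3 allows an unblinded injector to elicit, grade and filter adverse events, contrary to 5.2, and no section requires relatedness to be judged blind. The conclusion rests on reading the treating clinician at the second-injection visit as the injector, which is natural but not stated. It is clearest at that visit and weaker at 3 months.

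The size of any bias cannot be estimated from the documents. It is tempting to put a multiple on the difference in recorded events between arms, but such a multiple would simply be the ratio of two assumed attribution rates, and the documents support neither. With rare events and about 42 participants per arm, the absolute numbers affected are likely to be small. The case for change is that the contradiction is plain, sites cannot settle it for themselves, and the procedure could carry over into the definitive trial.

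**What to change.** - **Elicitation and grading.** In 7.2.3, replace the treating clinician with a blinded clinical member of the site team other than the injector, at both the second-injection and 3-month visits. At the second-injection visit this is done in person or by phone before the dose is prepared.
- **Relatedness.** State in 7.2.2 and 7.2.3 that relatedness is judged by a medically qualified investigator who is blinded to allocation.
- **Hand-over.** An event that the injector hears of is passed to the blinded assessor without the allocation. The injector otherwise records only procedural facts on the injection treatment log.
- **Recording condition.** Reconcile the relatedness condition in 7.2.3 with Tables 2 and 3, so that one definition decides which events of grade 3 or above enter the data.

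The rule on withholding the second injection, emergency code break (section 5.4) and unblinding for SUSAR reporting (section 7.2.5) are not affected.

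The cost is a protocol amendment, a line in site training and a short contact with a blinded clinician before each second injection. Section 5.2 already keeps site staff other than the injector and pharmacy blinded, and section 7.2.2 already requires a medically qualified assessor. The practical burden is having a blinded clinician reachable at that time, which may take some planning at services run largely by specialist practitioners (section 4.1).
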